**LIST OF ABBREVIATIONS AND RELEVANT DEFINITIONS**

ABR	ABR form, General Assessment and Registration form, is the application form that is required for submission to the accredited Ethics Committee (In Dutch, ABR = Algemene Beoordeling en Registratie)
AE	Adverse Event
AR	Adverse Reaction
CA	Competent Authority
CCMO	Central Committee on Research Involving Human Subjects; in Dutch: Centrale Commissie Mensgebonden Onderzoek
CGM	Continuous Glucose Monitoring
CV	Curriculum Vitae
DSMB	Data Safety Monitoring Board
EU	European Union
EudraCT	European drug regulatory affairs Clinical Trials
GCP	Good Clinical Practice
GLP-1	Glucagon-like peptide-1
HOMA-ir	Homeostatic model assessment of insulin resistance
IB	Investigator's Brochure
IC	Informed Consent
IMP	Investigational Medicinal Product
IMPD	Investigational Medicinal Product Dossier
METC	Medical research ethics committee (MREC); in Dutch: medisch ethische toetsing commissie (METC)
NQplus	Nutrition Questionnaires plus study
PYY	Peptide YY
(S)AE	(Serious) Adverse Event
SCFA	Short Chain Fatty Acid
SPC	Summary of Product Characteristics (in Dutch: officiële productinformatie IB1-tekst)
Sponsor	The sponsor is the party that commissions the organisation or performance of the research, for example a pharmaceutical company, academic hospital, scientific organisation or investigator. A party that provides funding for a study but does not commission it is not regarded as the sponsor, but referred to as a subsidising party.

SUSAR	Suspected Unexpected Serious Adverse Reaction
T2DM	Type 2 diabetes mellitus
Wbp	Personal Data Protection Act (in Dutch: Wet Bescherming Persoonsgegevens)
WF	Whole Fiber
WMO	Medical Research Involving Human Subjects Act (in Dutch: Wet Medisch-wetenschappelijk Onderzoek met Mensen)

## SUMMARY

**Rationale:** Dietary fibre intake is usually lower than recommended and dried vegetable can be a useful additional source. This may improve glucose metabolism by changes in microbiota composition.

**Objective:** To study the effect of WF Fibre on (continuous) glucose metabolism and potential underlying mechanisms, body weight and waist circumference, microbiota composition and fasting GLP1/PYY, in subjects with pre-diabetes.

**Study design:** Randomised placebo controlled single-blind parallel study

**Study population:** Human volunteers with pre-diabetes (n=60)

**Intervention (if applicable):** One group receives daily a dose of 30g of WholeFiber (WF fibre) and the other group 16g maltodextrin (placebo) for 21 days.

**Main study parameters/endpoints:** Changes in fasting insulin and HOMA-ir are the primary outcomes of the study. Changes in mean glucose and glycemic variability from continuous glucose monitoring, body weight, waist circumference, microbiota composition, breath hydrogen, GLP-1/PYY and SCFAs are the secondary outcomes.

**Nature and extent of the burden and risks associated with participation, benefit and group relatedness:** The intervention is therapeutic for half of the participants and non-therapeutic to the other half of the participants. The risk associated with the participation is negligible and the burden can be considered as minimal. At screening the following measurements and questionnaires will be taken: inclusion and diabetes risk score questionnaire (1x) food frequency questionnaire for fibre intake (1x), height (1x), weight (1x), fasting blood glucose (finger prick). During the intervention period over 3 weeks, with an additional 2 week run-in period and a 2 week wash-out period, subjects will take dietary supplements on the morning of each day of the intervention period, and come to the university on 4 occasions. During this 7 week period the following measurements will be taken: body weight (3x), fasting blood sample (2x), fasting breath sample (2x), continuous glucose monitoring (28 days), faecal samples (4x), wellbeing diary (49 days).

## 1. INTRODUCTION AND RATIONALE

Obesity and type 2 diabetes mellitus (T2DM) are worldwide expected to rise exponentially, with increasing health care costs and reduction in life expectancy and quality of life. We have recently shown that diabetes prevention is possible in real-life settings, by improving diets (such as whole-wheat bread and pasta) and increasing physical activity over a one-year period (Duijzer et al., 2017; den Braver et al., 2017)

Despite national recommendations to increase vegetable and fruit intake and intake of whole grain foods the habitual intake of dietary fibre is still low in the Netherlands (20-25 g/d compared to 35 g/d or more recommended) as well as in many other Western countries. Several observational studies, including our own (InterAct Consortium, 2015), have shown that subjects with higher fibre intake at reduced risk of developing obesity, and T2DM.

The underlying mechanisms have not been completely elucidated, but the intestinal microbiota may play an important role, for example by fermentation of fibre, modulation of microbiota composition and its activities, and specifically the resulting production of anti-inflammatory short chain fatty acids (SCFA) that via the release of incretins (GI hormones) PYY and GLP-1 directly stimulate insulin secretion by the beta-cell (DeClerq et al., 2017). Note that animal experiments have shown that modifying rodents' microbiota through faecal transplantation results in alterations of GI hormones and subsequently an altered metabolism (DeClerq et al., 2017). However, whether and to what these results relate to human metabolism is yet unclear. Earlier work of our group has shown that fibres, such as pectin, impact satiety and energy intake on the short-term (Wanders et al., 2011; Wanders et al., 2014).

Recent studies have indicated that there is a strong correlation between the intestinal microbiota and response to specific dietary compounds. A comparative study with various fibres in obese men with metabolic syndrome showed a marked individual response that related to their faecal microbiota composition (Salonen et al., 2014). A multicentre analysis revealed specific microbiota signatures that explained the responses of metabolic syndrome subjects to a variety of interventions, including resistant starch and inulin (Korpela et al., 2014). A further development derived from a large intervention study that used a machine-learning approach to mine personal health profiles that included microbiome data to predict the postprandial glycaemic response (Zeevi et al., 2015). A recent start-up is exploiting this and providing dietary advice based on the microbiota composition (daytwo.com). Hence, in fibre intervention studies it is of great interest to determine the faecal microbiota signatures that are present in the volunteers before and after the treatment in order to advance our knowledge and link these to the intervention success.

Recently, an interesting and natural food product (WholeFiber™) (WF) has been developed by WholeFiber Holding INC, that is based on whole vegetables, consisting of prebiotic fibres (85% on solids, consisting of inulin, pectin, hemicellulose and cellulose). This could be a useful addition to the general (Western) diet. It has a low ecologic footprint, and we propose that it can be used as a functional ingredient and a dietary supplement, alleviate deficiencies in dietary fibre intake and support a diverse gut microbiome, with subsequent prevention of delay of pre-diabetes. We propose as dose of 30g per day (approximately 25g fibre, the majority of which is inulin), in line with previous studies with inulin or inulin-type fructans (Dewulf et al.,

2013; Guess et al., 2016). To increase tolerance a dose escalation run-in period will be implemented (Guess et al 2016). We selected a parallel randomised intervention study in metabolic syndrome adults since cross-over studies suffer from intestinal microbiota adaptations (Salonen & De Vos, 2014).

This study will show whether WF can affect insulin resistance, continuous glucose metabolism and/or the microbiome during a three week period in subjects with elevated risk for developing type 2 diabetes mellitus. This will provide more insight in the potential health effects of a dried vegetable fibre and leads for the potential underlying metabolic changes including microbiota changes.

## **2. OBJECTIVES**

The objective of the VEZEL-studie is to study the effect of WF fibre on insulin resistance, (continuous) glucose metabolism, body weight, waist circumference, microbiota composition and breath hydrogen in subjects with pre-diabetes.

### Primary Objective:

To compare 3-week changes in fasting insulin level and HOMA-ir between subjects with pre-diabetes consuming either 30g of WF or 16g of placebo carbohydrate (maltodextrin).

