### 3. STUDY DESIGN

The study is designed as a single blind, randomised placebo controlled parallel trial in which 2 groups of 30 subjects receive either 30g of WF or 16g of control carbohydrate (maltodextrin, in iso-caloric amount) for a period of 3 weeks (21 days). To reduce potential gastrointestinal side effects of WF, the study will start with a 2 week run-in period during which time WF will be taken at 15g/day for 2 weeks before the actual intervention starts. The control arm will receive MD 8g/day during this period, an iso-caloric amount. The study schedule is summarized below. During the pre-study screening visit a fasting blood glucose measurement will be done using finger-prick and the Dutch diabetes risk score (DRS) will be assessed (<http://www.kijkopdiabetes.nl/professionals/diabetes-risicotest-3>).

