**Table 1. Study schedule VEZEL studie**

	Pre study screening	Before run-in	Run-in 14 days		Intervention 21 days		Wash-out 14 days		
		Day -17	Day -14		Day 1		Day 22		Day 35
Visit number →	1	2			3		4		
Home visit number →			1						2
Activity									
Informed consent	X								
Health questionnaire	X								
Diabetes risk score	X								
Finger prick (fasting glucose)	X								
Food frequency questionnaire	X								
Wellbeing diary			X	X	X	X	X	X	X
Handing out study sachets			X		X				
Return study sachets – compliance check					X		X		
Fasting blood sampling		X					X		
Stool collection			X		X		X		X
Fasting breath sample		X					X		
Continuous glucose monitoring		X	X	X until day -3	X	X until day 14			
Body weight / Waist circumference	X	X			X		X		
Body height	X								
Breakfast	X	X					X		
Post study screen									X
End of trial									X

X: CGM will be placed on the upper arm, device works for 14 days

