### 8.3 Study procedures

The volunteers will have a pre-study screening before the start of the intervention. This will involve:

- assessment of medical history
- assessment of Diabetes Risk Score (kijkopdiabetes.nl)
- assessment of regular fibre intake measured with a specific food frequency questionnaire
- measuring height, weight, waist circumference
- measuring fasting glucose from finger prick

For the timing of the procedure, see Table 1 in the Chapter Study Design. For logistic reasons subjects will be divided in two groups, starting their treatment period on two consecutive days. For both series the first day of treatment will be specified as Day 01.

During the main part of the intervention the subjects will consume 30 grams of WF fibre or 16 grams of placebo per day, for 21 consecutive days. Before starting, a fasting venous blood sample (total 30ml) will be taken to determine fasting blood glucose and insulin concentrations, and body weight and waist circumference will be measured. Subjects are asked to provide a stool sample for microbiota determination. For this, the participants will receive a home sampling kit with instructions from the WU Laboratory of Microbiology. Also a continuous blood glucose meter will be placed. Also a fasting breath sample will be obtained.

A run in period of 2 weeks on 15 gram WF fibre or 8 grams of placebo will precede the trial to avoid gastro-intestinal discomfort. After that, and before starting the main phase of the intervention, another stool sample will be asked for.

After 21 days of intervention with the full dose, a fasting blood sample, a stool sample, a breath sample and data on body composition will be obtained. After another 14 days of wash-out a final stool sample will be obtained. During the 49 days study period (2+3+2 weeks of run-in, intervention and wash-out resp.) a diary on abdominal side effects will be kept.

Compliance will be assessed by asking subjects to return unused and opened non-empty sachets.

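### The primary objective promises a 3-week change in fasting insulin and HOMA-ir, but the two blood samples span 38 days and 35 days of randomised product

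*Protocol*

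**What the plan says.** The primary objective in Protocol section 2 is "To compare 3-week changes in fasting insulin level and HOMA-ir between subjects with pre-diabetes" on 30 g WF or 16 g maltodextrin. The secondary objectives use the same 3-week wording for CGM measures, weight, waist, GLP-1/PYY, SCFA, breath hydrogen and microbiota. The last paragraph of section 1 also says the study will show whether WF has an effect "during a three week period in subjects with elevated risk for developing type 2 diabetes mellitus".

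The Summary budgets two fasting draws, "fasting blood sample (2x)". In Table 1 the row "Fasting blood sampling" is marked on Day -17 (Visit 2, before the run-in) and on Day 22 (Visit 4). It is empty on Day 1 (Visit 3). The breath-sample row has the same two marks.

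Section 3 states that "WF will be taken at 15g/day for 2 weeks before the actual intervention starts", and that the control arm takes 8 g/day of maltodextrin over the same two weeks.

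Section 8.3 says "For both series the first day of treatment will be specified as Day 01". It then describes the full-dose phase and continues: "Before starting, a fasting venous blood sample (total 30ml) will be taken to determine fasting blood glucose and insulin concentrations". The run-in comes in the next paragraph, followed by: "After that, and before starting the main phase of the intervention, another stool sample will be asked for".

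Section 10.1 adjusts end-line insulin or HOMA-ir for its baseline value without naming the baseline visit. Section 10.2 applies similar methods to the secondary outcomes.

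**The concern.** A change over the 3-week full-dose phase needs a value at the start of that phase. For insulin and HOMA-ir there is none. The only earlier venous sample is taken before a run-in in which the two arms take different products, so the run-in is part of the randomised exposure and not a neutral lead-in.

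The primary result would therefore be reported as the effect of three weeks on 30 g, when it is the effect of a stepped regimen lasting five weeks. That affects any conclusion about how quickly, and at what dose, WF acts.

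Section 8.3 adds uncertainty. It dates the first treatment day as Day 01 although product starts with the run-in, and it mentions the baseline draw directly after describing the full-dose phase. Section 10 does not settle which visit is the baseline. This matters for weight, waist and stool, which are measured both before any product and on Day 1.

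**Working it through.** **Inputs**

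- Blood and breath sampling days: Day -17 and Day 22 (Table 1).
- Run-in: 14 days at 15 g WF or 8 g maltodextrin per day (section 3).
- Full-dose phase: 21 days at 30 g or 16 g per day (sections 3 and 8.3).
- Sample size: SD of change 37 pmol/L; differences of 34 and 29 pmol/L; two-sided 5%; 80% power; 10% drop-out (section 4.5).

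**1. The plan's own sample size reproduces.** With a two-sample t-test:

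- 34/37 = 0.92 gives 19.6, so 20 per arm (40 in total).
- 29/37 = 0.78 gives 26.5, so 27 per arm (54 in total).
- 54/(1 - 0.10) = 60.

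None of these figures uses the length of the interval, so relabelling the interval leaves them as they are.

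**2. Length of the measured interval.** A 14-day run-in between Day -14 and Day 1 implies that there is no Day 0.

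- Day -17 to Day -14: 3 days without product.
- Day -14 to Day 1: 14 days of run-in.
- Day 1 to Day 22: 21 days at full dose.
- Total: 3 + 14 + 21 = 38 days, or 38/7 = 5.4 weeks. If there were a Day 0 it would be 39 days.

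**3. Exposure within that interval.**

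- Dosing days: 14 + 21 = 35, of which the run-in is 14/35 = 40%.
- WF: 14 × 15 = 210 g and 21 × 30 = 630 g, so the run-in share is 210/840 = 25%.
- Maltodextrin: 14 × 8 = 112 g and 21 × 16 = 336 g, so the run-in share is 112/448 = 25%.

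**4. Outcome by outcome: does a Day 1 to Day 22 change exist?**

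| Outcome | Sampled (Table 1) | 3-week change available? |
|---|---|---|
| Insulin, HOMA-ir | Day -17, Day 22 | No |
| Breath hydrogen | Day -17, Day 22 | No |
| GLP-1/PYY, SCFA | Same blood draws (assumed; Table 1 has one venous row) | No |
| Weight, waist | Screening, Day -17, Day 1, Day 22 | Yes, but Day 1 follows 14 days of arm-specific product |
| Stool | Day -14, Day 1, Day 22, Day 35 | Yes, with the same caveat |
| CGM | Day -17 to Day -3; Day 1 to Day 14 | No |

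For CGM, only about 3 days of the first window (Day -17 up to Day -14) are free of product. The rest lies in the run-in, and the second window ends on Day 14, before the full-dose phase is over.

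The screening finger prick cannot fill the gap: it gives capillary glucose only, with no insulin.

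**The case against.** The strongest reply is that nothing in the comparison is invalid. Day -17 precedes all product, and section 10.1 compares end-line values adjusted for baseline, which is a sound randomised contrast of the complete regimen. The run-in is openly described in the Summary, sections 1, 3 and 8.3, and Table 1, so a careful reader can see the 2 + 3 week exposure and may take the 3-week wording as shorthand for the full-dose phase. All of this stands, and it limits the point to the estimand and its label. It does not rescue the label. The objective states a change over a period whose starting value is never measured, and it attaches that change to the full dose.

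A reader might go further and infer from section 8.3 that the insulin baseline is drawn on Day 1, so that adjusting for an already treated value removes part of the effect and costs power. The documents do not support this. Table 1 has no blood draw on Day 1, the Summary allows two draws in all, and section 8.3 refers to Table 1 for timing. Section 8.3 also groups the draw with the CGM placement and the first stool sample, and adds only another stool sample after the run-in. Its wording is loosely ordered, but it does not set a Day 1 baseline for insulin.

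A reader might also infer that weight and waist will be adjusted for Day 1. The protocol does not say so. It leaves the visit open, and the reference to methods similar to the primary analysis favours the pre-run-in value.

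**Conclusion.** The primary objective is wrong as written. For insulin, HOMA-ir and breath hydrogen a 3-week change cannot be computed from the scheduled samples; the same holds for GLP-1/PYY and SCFA if they come from the same draws. The measured effect spans 38 days and 35 dosing days, with 40% of the dosing days and 25% of the WF falling in the run-in.

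The consequence is a misstated estimand and a misstated conclusion about duration and dose. It is not bias: the ANCOVA on the Day -17 value is an unbiased randomised comparison of the whole regimen. The sample size of 54, raised to 60, is unaffected, and no loss of power is claimed.

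This rests on two readings: that Table 1 governs the sampling days, and that randomisation precedes Day -14. The protocol does not date randomisation, but the run-in products differ by arm.

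**What to change.** 1. **Sections 1 and 2 (rationale, primary and secondary objectives).** Replace the 3-week wording for insulin, HOMA-ir and the other blood and breath outcomes. Define each as the Day 22 value adjusted for the pre-run-in Day -17 value, reflecting the 2-week run-in plus the 3-week full-dose phase.
2. **Section 8.3.** Tie the baseline venous and breath samples explicitly to the Day -17 visit of Table 1. Reconcile the statement that treatment starts on Day 01 with the run-in.
3. **Sections 10.1 and 10.2.** Name the pre-product value as the baseline covariate: Day -17, or the first stool sample for microbiota. Treat Day 1 weight, waist and stool as interim values, because they follow two weeks of arm-specific product.
4. **CGM.** Give it its own statement of what is compared with what. Acknowledge that only about 3 days of the first window are product-free and that the two windows do not yield a 3-week change.

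The cost is protocol wording, with no extra visit or sample and no change to the sample size. The downside is a changed claim: the trial can speak to a 5-week stepped exposure, and not to 3 weeks at full dose. A Day 1 blood sample would be needed only if a change over the full-dose phase itself were wanted, and that starting value would already be affected by treatment.

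### The primary objective is a 3-week change in fasting insulin and HOMA-ir at the full amount, but blood is drawn only on Day -17 and Day 22, so the trial measures the whole run-in plus intervention regimen

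*Protocol*

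**What the plan says.** Section 2 sets the primary objective as "To compare 3-week changes in fasting insulin level and HOMA-ir between subjects with pre-diabetes consuming either 30g of WF or 16g of placebo carbohydrate". The last paragraph of section 1 makes the matching promise: "This study will show whether WF can affect insulin resistance, continuous glucose metabolism and/or the microbiome during a three week period".

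Table 1 marks the row "Fasting blood sampling" in two columns only, Day -17 and Day 22. The Summary agrees on the count: "body weight (3x), fasting blood sample (2x), fasting breath sample (2x".

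Between those two days both arms take product at two levels. Section 3 describes a "2 week run-in period during which time WF will be taken at 15g/day for 2 weeks before the actual intervention starts", and adds: "The control arm will receive MD 8g/day during this period, an iso-caloric amount". In the main phase, according to section 8.3, "the subjects will consume 30 grams of WF fibre or 16 grams of placebo per day, for 21 consecutive days".

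On the baseline draw, section 8.3 says: "Before starting, a fasting venous blood sample (total 30ml) will be taken to determine fasting blood glucose and insulin concentrations". This follows directly after the sentence on the 21-day phase and gives no day number. Section 10.1 adjusts for baseline insulin or HOMA-ir, also without saying which day baseline is.

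**The concern.** The objective names an interval (three weeks) and an exposure (30 g WF or 16 g maltodextrin). The only two insulin measurements enclose a longer interval and a stepped exposure. The run-in is not a neutral lead-in: it is arm-specific, so any effect that develops during it is part of the measured treatment difference.

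At stake is what the primary result may be said to show. Reported in the words of the objective, a difference would be credited to three weeks at the full amount although it arose over five weeks of product at two levels. A reader who wants to use or compare the result would take the wrong duration and exposure from it.

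**Working it through.** **1. Can a three-week change be calculated?** Fasting insulin needs a venous sample.

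| Occasion | Venous blood (Table 1) | Other relevant collection |
|---|---|---|
| Screening | none | finger prick, glucose only |
| Day -17 | yes | breath, weight, waist |
| Day -14 | none | stool; first sachets handed out |
| Day 1 | none | stool, weight, waist |
| Day 22 | yes | stool, breath, weight, waist |

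The Summary's count of two samples matches. For the point between run-in and main phase, the text of section 8.3 names a stool sample and no blood. Three places therefore agree, so this is unlikely to come from the way the table was extracted. Baseline insulin and HOMA-ir can only be the Day -17 values.

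**2. What lies between the samples?** Inputs: Table 1 for days; sections 3 and 8.3 for amounts.

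- Calendar interval: Day -17 to Day 1 is 17 days and Day 1 to Day 22 is 21 days, so 17 + 21 = 38 days, or 38/7 = 5.4 weeks. This assumes no Day 0, since Day -14 to Day -1 already makes the stated 14 run-in days. With a Day 0 it would be 39.
- Product days: 14 + 21 = 35, or 5 weeks. Share in the run-in: 14/35 = 40%.
- WF planned: 14 × 15 + 21 × 30 = 210 + 630 = 840 g. Share in the run-in: 210/840 = 25%.
- Maltodextrin planned: 14 × 8 + 21 × 16 = 112 + 336 = 448 g. Share in the run-in: 112/448 = 25%.

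**3. Does this touch the sample size?** Section 4.5 was reproduced with a two-sample t-test (noncentral t, two-sided 5%, 80% power, SD of change 37 pmol/L):

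- 34/37 = 0.919 gives 19.6, so 20 per arm, 40 in total (power 80.8%). This matches.
- 29/37 = 0.784 gives 26.5, so 27 per arm, 54 in total (power 80.7%). This matches.
- 54/0.9 = 60. This matches.

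No interval or product amount enters these formulas, so restating the time frame leaves 60 unchanged.

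**4. Which other outcomes share the problem?** The Secondary Objective uses the same three-week wording. GLP-1/PYY and SCFA depend on the fasting blood samples, and the breath row in Table 1 is also marked only on Day -17 and Day 22. For these, too, no change from Day 1 exists. Weight, waist and stool are collected on Day 1, so a three-week change can be calculated for them.

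**The case against.** The strongest reply is that only a label is at fault. The arms receive different products from the start of the run-in, and the Day -17 sample precedes any product, so the comparison from Day -17 to Day 22 is an intact randomised contrast. The run-in amounts and duration are openly described in section 3, Table 1 and section 8.3, and the Summary calls the run-in additional to the three weeks. All of this stands, and it limits the weight of the point. It does not remove the contradiction, because the objective still names a quantity that the schedule cannot supply.

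A reader might infer more from the documents than they support:

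- *That staff will draw the baseline on Day 1.* The sentence order in section 8.3 is clumsy, but that section refers to Table 1 for timing, Table 1 has no Day 1 blood, and the text later names only stool at that point. A Day 1 draw would be a departure from the protocol, not something it provides for.
- *That power is lost because part of the effect falls in the run-in.* This needs a Day 1 draw and, in addition, an assumption about how the effect builds up with amount or time. The documents give no basis for such an assumption.
- *That weight, waist and microbiota lack a product-free baseline.* Table 1 has weight and waist on Day -17 and stool on Day -14, the day the first sachets are handed out.

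**Conclusion.** The point holds as an inconsistency between the objectives and the schedule. The three-week change in fasting insulin and HOMA-ir cannot be computed. The planned ANCOVA estimates the effect of a regimen of 35 product days, 14 at the run-in amount and 21 at the full amount, between samples about 38 days apart. Two fifths of the product days and a quarter of the planned product lie outside the three weeks that the objective names.

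The treatment contrast is not biased by this and the sample size does not change. The gram figures assume that planned amounts are taken in full, and the 38 days assume no Day 0. The conclusion depends on neither. It should be corrected because it concerns the primary objective and costs almost nothing.

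**What to change.** Reconcile the objectives with Table 1, and keep the schedule and the ANCOVA.

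- Primary Objective and the last paragraph of section 1: state the primary outcome as the change in fasting insulin and HOMA-ir from Day -17 (before product) to Day 22, across run-in plus intervention. Add the same time frame to the Summary, which now gives the primary outcome none.
- Secondary Objective: make the same change for GLP-1/PYY, SCFA and breath hydrogen.
- Section 8.3: date the first fasting blood sample as Day -17, before the run-in.
- Section 10.1: define baseline insulin and HOMA-ir as the Day -17 values.
- Reporting: word the conclusion for the run-in plus intervention regimen, not for three weeks at 30 g.

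The cost is a few sentences in six places, with no new samples and no extra participants. The one downside is a slightly less attractive claim: five weeks of product in two steps instead of three weeks at one level.
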